1. SYNOPSIS

Protocol Title: A Two Part Study to Assess the Relative Bioavailability and Food Effect of a Novel Tablet Formulation of Boosted-GSK2838232 Compared to Capsule as well as the Safety and Pharmacokinetics of Repeated Once-Daily Doses of Non-boosted GSK2838232

Short Title: A two-part study to i) compare a tablet and capsule formulation of GSK2838232 with and without food, and ii) assess the safety and pharmacokinetics of repeated once-daily doses of GSK2838232 without ritonavir.

Rationale:

This will be a two-part study design that will confirm the acceptability of a tablet formulation in healthy participants for future clinical development of GSK2838232.

Part 1 is a relative bioavailability study that will assess single ritonavir (RTV)-boosted doses of a novel tablet formulation given with food (normal, approximately 30% fat) against the reference capsule formulation also given with food (Part 1A) and then will assess the impact of fasted conditions on the tablet performance (Part 1B).

Part 2 is a study of non-boosted GSK2838232, given as once-daily tablet doses for 11 days in a separate cohort of participants, assuming the tablet performance is considered acceptable from Part 1A. The dose of GSK2838232 used in Part 2 will be confirmed after Part 1A but is likely to be, and will not exceed, 500 mg once daily (QD) as tablets.

Objectives and Endpoints:

Part 1:

Objectives	Endpoints							
Primary								
To assess the relative bioavailability of a novel GSK2838232 tablet formulations versus the capsule formulation (Part 1A)	• AUC(0-∞) and Cmax							
To assess the effect of food on GSK2838232 exposure of the tablet formulation (Part 1A and Part 1B)	• AUC(0-∞), Cmax, and tmax							

Objectives	Endpoints
Secondary	
To investigate the safety and tolerability of GSK2838232 following single dose administration as tablets or capsules, with RTV	GSK2838232 safety parameters: adverse events; absolute values and changes over time of clinical laboratory evaluations (hematology, clinical chemistry, urinalysis), vital signs, and 12-lead electrocardiogram (ECG) parameters from pre-dose values
To characterize the pharmacokinetics of GSK2838232 after administration of a novel tablet formulation and capsule formulation with food, and the tablet formulation given without food	• tlag, tmax, t½, tlast, C24, and AUC(0-t)

Part 2:

Objectives	Endpoints
Primary	
To assess the safety of GSK2838232 administered as non-boosted once-daily doses of a tablet formulation for 11 days	GSK2838232 safety parameters: adverse events; absolute values and changes over time of clinical laboratory evaluations (hematology, clinical chemistry, urinalysis), vital signs, and ECG parameters from pre-dose values
To assess the pharmacokinetics of GSK2838232 administered as non-boosted once-daily doses of a tablet formulation for 11 days	 Day 1 dose: AUC(0-τ), Cmax, Cτ, tmax, tlag Day 11 dose: AUC(0-τ), AUC(0-∞), Cmax, Cτ, tmax, t½, tlast
Secondary	1
To assess time to steady-state of GSK2838232 when administered as non-boosted once-daily doses of a tablet formulation for 11 days	Pre-dose concentrations on Days 2 to 11
To assess accumulation of GSK2838232 when administered as non-boosted once-daily doses of a tablet formulation for 11 days	• Accumulation ratios: Ro[AUC(0-τ)], R(Cmax), R(Cτ)

AUC(0- τ) = Area under the curve (Area under the plasma drug concentration-time curve from pre-dose to the end of the dosing interval at steady state); AUC(0-inf)= Area under the concentration-time curve from time zero (pre-dose) extrapolated to infinite time; Cmax= Maximum observed concentration; t1/2= Apparent terminal phase half-life; tmax= Time of occurrence of Cmax; tlag= Lag-time (time delay between drug administration and first observed concentration above LOQ in plasma); AUC (0-t) = Area under the concentration-time curve from zero up to a definite time t

Overall Design

Part 1:

Part 1 is a relative bioavailability study that will further subdivide into two parts (Part 1A and Part 1B) (Table 1). In Part 1A, the safety and pharmacokinetics (PK) of a novel tablet formulation of GSK2838232 will be evaluated in open label, randomized, cross-over fashion against the capsule formulation as reference. Each actual treatment dose will be separated by a minimum 10-day washout period. Part 1A will be studied in the fed state using a normal fat (i.e., approximately 30%) meal in all participants. In Part 1B, the tablet will be administered in the fasted state to understand the impact of food on relative bioavailability.

Table 1 Treatment Groups in Part 1

Sequence	N	Part 1A		Part 1B				
		Period 1	Period 2	Period 3				
1	6	A	В	С				
2	6	В	A					

- 1. All treatments in Part 1A to be administered with RTV in a fed state, following two RTV pre-doses.
- 2. There will be a washout of at least 10 days between each Period.
- 3. Treatment A = $GSK2838232\ 200\ mg/r$ (as 4 x 50 mg) capsule formulation, fed, normal fat (i.e., approximately 30%) meal (reference).
- 4. Treatment $B = GSK2838232\ 200\ mg/r$ (as $2\ x\ 100\ mg$) tablet formulation, fed, normal fat (i.e., approximately 30%) meal.
- 5. Treatment C = GSK2838232 200 mg/r (as 2 x 100 mg) tablet, confirmed from Part 1A, fasted.

After completion of Part 1A, preliminary PK data will be analyzed, and a decision will be made based on safety, tolerability, relative bioavailability PK criteria, as well as feasibility considerations, as to whether the tablet formulation will be used to conduct Part 1B (fasted) and Part 2.

Part 2:

Part 2 will evaluate non-RTV boosted GSK2838232, given as single daily doses for 11 days in a separate cohort of participants (N=8; 6A/2P). The placebo tablet supplied will not be identical to GSK2838232 and as such will be administered by site staff via an opaque card/paper tube to facilitate the single blind (i.e., the Principal Investigator [PI] and the participants themselves will be blinded as to their treatment). The dose chosen for Part 2 will depend upon the preliminary results of the tablet in Part 1A but is likely to be, but will not exceed, 500 mg (i.e., 5 x 100 mg tablets) QD.

Number of Participants:

It is expected that a sufficient number of participants will be screened in order to enroll approximately 16 healthy participants to provide at least 12 evaluable participants through the three study periods for Part 1 and 10 healthy participants to provide at least 8 evaluable participants for the single study period of Part 2.

If participants prematurely discontinue the study, additional participants may be randomized and assigned to the same treatment sequence at the discretion of the Sponsor in consultation with the Investigator.

[figure not shown]
Treatment Groups and Duration:

GSK2838232 as tablets or capsules (at a 200 mg dose level) will be administered with 100 mg RTV, after two pre-doses of 100 mg RTV QD over 48 h. The use of RTV priming is an aspect of GSK2838232 clinical development (specifically relative bioavailability studies) so far and allows a more accurate assessment of what will ultimately happen in the repeat-dose clinical studies with GSK2838232 when administered with RTV. In Part 2 of the study however, GSK2838232 will be administered unboosted and no RTV will be co-administered.

In both Part 1 and Part 2 participants will have a screening visit within 30 days prior to first dose, a minimum 10-day washout period between doses (Part 1 only), and a follow-up visit 7 to 14 days after the last dose. The maximum duration of study participation will be approximately 9 to 10 weeks for Part 1 and 8 to 9 weeks for Part 2.

Study Schematic

[figure not shown]
Part 1

Treatments A and B will be Capsule and Tablet administered in a randomized crossover design with 100 mg Ritonavir with food (fed state) (Part 1A).

Treatment C will be Tablet assessed in Part 1A, administered with 100 mg Ritonavir without food (fasted state) (Part 1B)

Part 2

2. SCHEDULE OF ASSESSMENTS

Please see Table 2 and Table 3 below for the Schedule of assessments for study Parts 1 and 2 respectively.

Table 2 Schedule of Assessments for Part 1A and Part 1B: Single Dose RBA \pm Food

	Screening (within 30 days of	Periods 1 through 3													
Procedure	Day 1 - carried out over multiple days – except as noted in	Day -3	Day -2	Day -1	Day 1	Day 2	Day 3	Day 4	Day 5	Day 6	Day 7	7-14 days			
	footnotes)					24 h	48 h	72 h	96 h	120 h					
Admission to Unit	,	X2													
Outpatient Visit	Х											Х			
Informed Consent	Х														
Medical/medication/															
drug/alcohol history (Demographics)	X														
Full Physical Examination	Х														
Brief Physical Examination			Х				Х					Х			
Height, Weight, BMI	Х														
Inclusion/Exclusion	Х														
Vital signs ³	Х		Х	Χ	Χ	Χ	Х	Χ				Х			
12 Lead ECG ⁴	Х		Х	Χ	Χ	Χ	Х					Х			
Echocardiogram ⁵	Χ														
Drug/alcohol/cotinine screen	Χ	Х													
HbsAg, HCV, HIV tests	Χ														
Hem/Chem/Urine tests ⁶	Х		Х	Х		Х		Х				Х			
Serum FSH (as appropriate)	Х														
Troponin I ⁷	Х			Х	Χ	Χ		X							
24 h Holter Monitoring ⁸	Х														
Pregnancy test (women)	Χ	Χ										Χ			
Run-in Dosing with RTV			X	Χ											
Dosing with GSK2838232+RTV					X										
PK Sampling ⁹					X	Χ	X	Χ	Χ	X					
Adverse Event Review ¹⁰				X	Х	Χ	Х	Χ	Х	Х	Χ	Х			
Con Med Review			X	Χ	Χ	Χ	X	Χ	Χ	X	Χ	X			
Discharge from Unit ¹¹						X									
Out Patient Visit							X	Х	X	Χ	Χ				

BMI = Body Mass Index; ECG = Electrocardiogram; FSH = Follicle Stimulating; HbsAg = Hepatitis B surface Antigen; HCV = Hepatitis C Virus; HIV = Human Immunodeficiency Virus; Hem/Chem = Hematology/Clinical Chemistry; RTV = Ritonavir; PK = Pharmacokinetic(s); Con Med = Concomitant medications.

- 1. Follow-up Visit to take place after Treatment Period 2.
- 2. When participants stay in the unit across treatment periods, drug/alcohol/cotinine screen and pregnancy test (women) are not required on Day -3 for later periods.
- 3. On Day 1, Blood pressure (BP) and Heart rate (HR) will be collected at pre-dose (triplicate) and single assessments at 1, 2, 4, 6, 8, 12, 24, 48, and 72 h post-dose.
- 4. On Day 1, 12-lead ECG will be collected at pre-dose (triplicate), and single assessments at 1, 2, 4, 6, 8, 12, 24, 48 and 72 h post-dose.
- 5. Echocardiograms must be within 100 days of Day 1.
- 6. Samples for Chemistry and Hematology: Blood samples will be obtained after an 8-hour fast.
- 7. Collect one troponin sample to be analyzed at local laboratory. A second sample will be collected, frozen and stored on site for potential high sensitivity troponin analysis.
- 8. 24-h Holter monitoring to be performed after confirming negative urine drug screen at screening, and must be within 30 days of Day 1. Holter monitoring on other days only if needed.
- 9. Plasma PK samples for bioanalysis for GSK2838232 will be collected pre-dose (within 15 minutes prior to dosing) and 0.5, 1, 1.5, 2, 2.5, 3, 3.5, 4, 6, 8, 12, 24, 36, 48, 72, 96, and 120 h post-dose. Samples will be acidified with an equal volume of 50 mmol citrate acid buffer pH 4.0.
- 10. An AE enquiry will be made at each visit, participants will be asked if they have experienced any neuropsychiatric adverse events, including psychosis or altered mental status. (see guidance for grading Altered Mental Status in Appendix 4).
- 11. Participants may be discharged after all study procedures are completed. Participants will be in house for PK blood samples on Day 3 (48 h), Day 4 (72 h), Day 5 (96 h) and Day 6 (120 h) of both study periods.

Table 3 Schedule of Assessments for Part 2: Repeated Doses for 11 days:

Management	Screening (within 30 days of Day 1 - carried out over	y															Follow- up		
Measurement	multiple days - except as noted in footnotes)	Day -1	Day 1	Day 2	Day 3	Day 4	Day 5	Day 6	Day 7	Day 8	Day 9	Day 10	Day 11 0 h	Day 12 24 h	Day 13 48 h	Day 14 72 h	Day 15 96 h	Day 16 120 h	7-14 days after last dose
Admission to Unit		Χ																	
Informed Consent	Х																		
Medical/medication/ drug/alcohol history (Demographics)	Х																		
Full Physical Examination	X													Х					
Brief Physical Examination		Х																	Х
Height, Weight, BMI	Х																		
Inclusion/Exclusion	Х																		
Medical History	Х																		
Vital Signs ¹	Х	Χ	Χ	Χ	Χ	Χ	Χ	Χ	Χ	Χ	Χ	Χ	Χ	Χ	Χ	Χ			Χ
12-lead ECG ²	Х	Χ	Χ	Χ	Χ		Х			Χ			X	Χ					Χ
Echocardiogram ³	Х																		
Drug/alcohol/ /cotinine Screen	Х	Х																	
HbsAg, HCV, HIV Testing	Х																		
Hem/Chem tests ⁴	Х	Χ		Х		Х		Х		Х			Х			Х			Х
Urinalysis	Х	Χ		Х		Х							Х			Х			Х
Serum FSH (as appropriate)	X																		
Troponin I ⁵	X	Χ	Х	Х			X			Χ			Х			Х			

Measurement	Screening (within 30 days of Day 1 - carried																		Follow- up
	out over multiple days - except as noted in footnotes)	Day –1	Day 1	Day 2	Day 3	Day 4	Day 5	Day 6	Day 7	Day 8	Day 9	Day 10	Day 11 0 h	Day 12 24 h	Day 13 48 h	Day 14 72 h	Day 15 96 h	Day 16 120 h	7-14 days after last dose
24 h Holter Monitoring ⁶	Х																		
Pregnancy Test (females)	X	Х																	Х
Dosing of GSK2838232			Х	Χ	Х	Х	Х	Х	Χ	Χ	Χ	Х	Х						
Plasma PK sampling ⁷			Х	Χ	Χ	Х	Χ	Χ	Χ	Χ	Χ	Χ	Χ	Χ	Х	Χ	Χ	Χ	
Adverse Event Assessment ⁸		Х	Х	Х	Х	Х	Х	Х	Х	Х	Х	Х	Х	Х	Х	Х	Х	Х	Х
Concomitant Medications		Х	Х	Х	Х	Х	Х	Х	Х	Х	Х	Х	Х	Х	Х	Х	Х	Х	Х
Discharge from Unit															X 9				
Out Patient Visit	Х															Χ	Χ	Χ	Χ

BMI = Body Mass Index; ECG = Electrocardiogram; FSH = Follicle Stimulating Hormone; HbsAg = Hepatitis B surface Antigen; HCV = Hepatitis C Virus; Hem/Chem = Hematology/Clinical Chemistry; HIV = Human Immunodeficiency Virus; IP = Investigational Product; PK = Pharmacokinetic(s).

- 1. A single blood pressure (BP) and Heart rate (HR) assessment will be collected at screening and Day -1. On Day 1 triplicate BP and HR will be collected at pre-dose and single assessments at 1, 4, 24, 48 and 72 h (Day 4) post-dose, Day 5, Day 6, Day 7, Day 8, Day 9, Day 10, Day 11 at pre-dose (triplicate), and single assessment at 1, 4, 24, 48 and 72 h post-dose, and at follow-up.
- 2. A single 12-Lead ECG will be collected at screening and Day -1. On Day 1 triplicate 12-Lead ECGs will be collected at pre-dose, and then single 12-Lead ECGs at 1, 4 and 12 h post-dose. Single 12-Lead ECGs will be collected on Days 2, 3, 5, 8. On Day 11 triplicate 12-Lead ECGs will be collected pre-dose, and then single 12-Lead ECGs collected at 1, 4, 12 and 24 h post-dose and at follow-up.
- 3. Echocardiograms must be within 100 days of Day 1.
- 4. Samples for Chemistry and Hematology: Blood samples will be obtained after an 8-hour fast.
- 5. Collect one troponin sample to be analyzed at local laboratory. A second sample will be collected and frozen for potential high sensitivity troponin analysis.
- 6. 24-h Holter monitoring to be performed after confirming negative urine drug screen at screening, and must be within 30 days of Day 1. Holter monitoring on other days only if needed.

- 7. Plasma PK samples for GSK2838232 will be collected as follows: Day 1; pre-dose (within 15 minutes prior to dosing) and 0.5,1, 1.5, 2, 2.5, 3, 3.5, 4, 6, 8, 12 and 24 h post-dose (prior to Day 2 dose). Days 3 to 10 pre-dose (within 15 minutes prior to dosing). Day 11; pre-dose (within 15 minutes prior to dosing) and 0.5, 1, 1.5, 2, 2.5, 3, 3.5, 4, 6, 8, 12, 24, 36, 48, 72, 96 and 120 h post-dose. Samples will be acidified with an equal volume of 50 mmol citrate acid buffer pH 4.0.
- 8. An AE enquiry will be made at each visit, participants will be asked if they have experienced any neuropsychiatric adverse events, including psychosis or altered mental status. (see guidance for grading Altered Mental Status in Appendix 4).
- 9. Participants will be discharged after all study procedures are completed on the morning of Day 13 (after the 48 h post-final dose sample time point) with instructions to return fasted on the mornings of Day 14 for 72 h PK sample, Day 15 for 96 h PK sample, and Day 16 for 120 h PK sample.

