6.3. Lifestyle Restrictions

6.3.1. Meals and Dietary Restrictions

Participants should avoid consumption of red wine, Seville oranges, grapefruit or grapefruit juice (and/or pomelos, exotic citrus fruits, grapefruit hybrids or fruit juices) from 5 days before the first dose of study medication, until follow-up.

Participants should refrain from eating poppy seed-containing food (e.g., poppy cake) at least 3 days before admission as this can falsify the urine drug screen. A positive illicit drug result will lead to exclusion from the remainder of the study.

• Water is allowed ad libitum throughout the study.

- While in residence in the clinical research unit (admission through discharge), participants will be restricted to food and beverage that is site-provided at specific times. Participants are expected to complete all meals and snacks (100%) within 25 minutes (Parts 1A and Part 1B). Non-compliance will be recorded.
- Participants will be fed a "normal" standardized diet consisting of an average between 3400 to 4000 kcal for each full day in residence (with the exception of Part 1B dosing days where dosing is conducted under fasted conditions). A 5% variance in calories is allowed. The macronutrient distributions and caloric criteria are within the recommendations in the *Dietary Guidelines for Americans*, 2010.

• Part 1A and Part 2

- Standardized meals will be provided to participants in Part 1A starting with Day 1 through discharge from the clinical research unit.
- Standardized meals and snacks should be completed within 25 minutes. Participants will be expected to complete all meals and snacks (100%). Non-compliance on Day 1 will be recorded in increments of 25% (e.g., 0%, 1-25%, 26-50%, 51-75% or 76-100% meal or snack completed).
- Participants will undergo at least a 10-hour overnight fast then will be provided a meal 30 minutes before dosing and will be expected to complete the meal within 25 minutes. Lunch will be provided approximately 4 hours after morning dosing and dinner will be provided approximately 9 hours after morning dosing. On Day 1, all participants will receive identical meals at breakfast, lunch, dinner and snack. On non-dosing days, meals will be served per the standard times at the clinical research unit.

• Part 1B (tablet, fasted):

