7.7. Concomitant Therapy

Any medication or vaccine (including over-the-counter or prescription medicines, vitamins, and/or herbal supplements) that the participant is receiving at the time of enrollment or receives during the study must be recorded along with:

- reason for use,
- dates of administration including start and end dates,
- dosage information including dose and frequency.

The Medical Monitor should be contacted if there are any questions regarding concomitant or prior therapy.

Participants must abstain from taking prescription or nonprescription drugs (including vitamins and dietary or herbal supplements) within 7 days (or 14 days if the drug is a potential enzyme inducer) or 5 half-lives (whichever is longer) before the start of study treatment until completion of the follow-up visit, unless, in the opinion of the Investigator and sponsor, the medication will not interfere with the study.

Acetaminophen, at doses of ≤ 2 g/day is permitted for use any time during the study. Other concomitant medication may be considered on a case by case basis by the Investigator in consultation with the Medical Monitor.

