9. STUDY ASSESSMENTS AND PROCEDURES

Each participant will have adequate time to provide informed consent of his or her own free will and before conducting any study procedures according to the International Conference on Harmonization (ICH) and Code of Federal Regulations (CFR) guidelines. Each participant will be provided a copy of the signed informed consent document (ICF) before the initiation of any study procedures.

After a participant has provided written informed consent and within 30 days of the first dose of study treatment, the Investigator or other study personnel will determine if the participant is eligible for enrolment in the study. This will be done by reviewing the inclusion and exclusion criteria and completing all of the screening assessments outlined in the Schedule of assessments Tables (Table 2 and Table 3). Screening assessments may be carried out over more than 1 day provided that all required assessments are completed within 30 days before the first administration of study treatment.

Protocol waivers or exemptions are not allowed with the exception of immediate safety concerns. Therefore, adherence to the study design requirements, including those specified in the Schedule of Assessments Tables (Table 2 and Table 3), are essential and required for study conduct.

Whenever vital signs, 12-lead ECGs and blood draws are scheduled for the same nominal time, the assessments should occur in the following order:

- 1. 12-lead ECG.
- 2. Vital signs.
- 3. Blood draws.

Note: The timing of the assessments should allow the blood draw to occur at the exact nominal time. In the event that the timing for a scheduled assessment conflicts with an

assessment that has to be repeated, the scheduled assessment will be performed on time/as scheduled and the repeat assessments will be conducted when feasible.

The timing and number of planned study assessments, including: safety and PK assessments may be altered during the course of the study based on newly available data (e.g., to obtain data closer to the time of peak plasma concentrations) to ensure appropriate monitoring.

The Institutional Review Board (IRB) will be informed of any safety issues that require alteration of the safety monitoring scheme or amendment of the Informed Consent Form.

The timing of planned study assessments is listed in the Schedule of Assessments Tables (Table 2 and Table 3).

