9.2. Adverse Events

The definitions of an AE or SAE can be found in Section 12.5, Appendix 5.

The Investigator and any designees are responsible for detecting, documenting, and reporting events that meet the definition of an AE or SAE and remain responsible for following up AEs that are serious, considered related to the study treatment or the study, or that caused the participant to discontinue the study treatment or study (see Section 8). In addition, all ventricular tachyarrhythmias are considered AEs of interest and should be reported to the Sponsor within 24 hours.

9.2.1. Time Period and Frequency for Collecting Adverse Event and Serious Adverse Event Information

- All SAEs will be collected from the signing of the ICF until the follow-up visit at the time points specified in the Schedule of Assessments Tables (Table 2 and Table 3).
- All AEs will be collected from the start of treatment until the follow-up visit at the time points specified in the Schedule of Assessments Tables (Table 2 and Table 3).
- The Sponsor will inform FDA within 7 days of any grade 2 or higher "alteration in personality-behavior or in mood" or "altered mental status" adverse events that occur in participants who have received GSK2838232.
- Medical occurrences that begin before the start of study treatment but after obtaining informed consent will be recorded on the Medical History/Current Medical Conditions section of the case report form (CRF) not the AE section.
- All SAEs will be recorded and reported to the sponsor or designee within 24 hours, as indicated in Section 12.5, Appendix 5. The Investigator will submit any updated SAE data to the sponsor within 24 hours of it being available.

- Investigators are not obligated to actively seek AEs or SAEs in former study participants. However, if the Investigator learns of any SAE, including a death, at any time after a participant has been discharged from the study, and he/she considers the event to be reasonably related to the study treatment or study participation, the Investigator must promptly notify the sponsor.
- NOTE: The method of recording, evaluating, and assessing causality of AEs and SAEs and the procedures for completing and transmitting SAE reports are provided in Section 12.5, Appendix 5.

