9.2.5. Pregnancy

- Details of all pregnancies in female participants and female partners of male participants will be collected after the start of study treatment and until the final follow-up visit.
- If a pregnancy is reported, the Investigator should inform GSK within 24 hours of learning of the pregnancy and should follow the procedures outlined in Section 12.6, Appendix 6.
- Abnormal pregnancy outcomes (e.g., spontaneous abortion, fetal death, stillbirth, congenital anomalies, ectopic pregnancy) are considered SAE.

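### Table 2 footnote 1 places the only Part 1 follow-up visit after Period 2, but the last dose for Part 1B participants is in Period 3

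*Protocol*

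**What the plan says.** Protocol Table 2 is the schedule for Parts 1A and 1B. Its columns cover Periods 1 to 3 and it has a single follow-up column. Footnote 1 states: "Follow-up Visit to take place after Treatment Period 2". SAP 14.2.1 reproduces the table and the footnote.

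The synopsis (Treatment Groups and Duration) and Section 5.1 (Part 1) both call for "a follow-up visit 7 to 14 days after the last dose". Section 7.3 gives the sequences as ABC and BAC, so the last dose is Treatment C in Period 3 for anyone who goes on to Part 1B. SAP 14.4.3 assigns AEs arising during follow-up to the Period 3 treatment, so it too treats follow-up as coming after Period 3. The synopsis adds: "The maximum duration of study participation will be approximately 9 to 10 weeks for Part 1".

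Section 9 says that the study design requirements, "including those specified in the Schedule of Assessments Tables (Table 2 and Table 3), are essential and required for study conduct".

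Other rules run to the follow-up visit:
- Section 9.2.1: "All AEs will be collected from the start of treatment until the follow-up visit"; SAEs have the same end point.
- Section 9.2.5: details of pregnancies "will be collected after the start of study treatment and until the final follow-up visit".
- Section 7.7: the ban on other drugs applies for a set interval "before the start of study treatment until completion of the follow-up visit".
- Section 6.3.1: the red wine and citrus restriction applies "from 5 days before the first dose of study medication, until follow-up".

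**The concern.** The footnote and the text give different dates for every participant dosed in Period 3, and the table offers only one follow-up visit. If the footnote is followed, the intended safety visit after the final boosted dose does not take place. That visit carries the brief physical examination, vital signs, ECG, laboratory tests, pregnancy test, AE review and concomitant medication review.

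Because the visit also closes AE and SAE collection, pregnancy reporting, the drug restriction and the citrus restriction, moving it forward would formally end all of these before or during Period 3. Period 3 supplies the fasted arm of the primary food-effect comparison. The date of this visit therefore needs to be unambiguous.

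**Working it through.** **Inputs.** Screening up to 30 days before first dose; minimum 10-day washout between doses; follow-up 7 to 14 days after the last dose (synopsis, Section 5.1). Within a period, Table 2 has admission on Day -3, ritonavir run-in on Days -2 and -1, dosing on Day 1, last laboratory tests on Day 4 (72 h) and last AE review on Day 7 (6 days after the dose).

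**1. The stated duration.** Follow-up after Period 3 at minimum washout: 30 + 10 + 10 + 14 = 64 days; 64 / 7 = 9.1 weeks, which agrees with the stated 9 to 10 weeks. Under the literal footnote the last scheduled contact is Period 3 Day 7: 30 + 10 + 10 + 6 = 56 days = 8.0 weeks. The washout is only a minimum. With 14-day dose intervals (an assumption) the totals are 30 + 14 + 14 + 14 = 72 days (10.3 weeks) and 30 + 14 + 14 + 6 = 64 days (9.1 weeks). The stated duration therefore does not decide between the two readings.

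**2. Where the footnote's visit would fall.** Put the Period 2 dose at d0. With a 10-day interval the Period 3 dose is at d10, so Day -3 = d7, Day 1 = d10 and Day 5 = d14. A visit at d7 to d14 would coincide with Period 3 Day -3 to Day 5, that is, with admission, run-in, dosing and early sampling. For a general interval w, admission is at d(w - 3), and at least one day of the window precedes it when w - 3 > 7, i.e. w of 11 days or more. The footnote could therefore be carried out in practice once the interval exceeds the minimum by a day.

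**3. What would be lost after the Period 3 dose.**
- Laboratory tests: the last are at 3 days. The intended visit comes 7 - 3 = 4 to 14 - 3 = 11 days later.
- AE review: the last is at 6 days. The intended visit comes 7 - 6 = 1 to 14 - 6 = 8 days later.
- Procedures: seven are marked at follow-up. Six also have a mark between Day 1 and Day 7. The pregnancy test does not; its other marks are screening and Day -3, and footnote 2 waives the Day -3 test in later periods for women who stay in the unit.

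**4. A secondary inconsistency in the same table.** The grid marks discharge on Day 2 and outpatient visits from Day 3. Footnote 11 and the Study Plan in Section 5.1 keep participants in the unit to the 120 h sample on Day 6. Footnote 11 also refers to *both* periods although the table has three. Together with footnote 1, this suggests wording left over from a two-period schedule.

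**The case against.** The synopsis and Section 5.1 state the right rule plainly, and SAP 14.4.3 agrees with them. Section 5.3 defines a completer as someone who has finished all phases including follow-up, which also implies a visit at the end. Section 9 binds sites to the design requirements generally, so it does not rank the table above Section 5.1. The footnote gives no day count, and a visit after Period 3 is, strictly, also after Period 2. If Part 1B is not run, the footnote is correct. At the minimum washout the overlap with Period 3 is so awkward that a site would probably query it. The heading of Table 2's follow-up column is truncated in the text available here; Table 3's refers to the last dose, and Table 2's may do so too.

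Much of this stands, and it limits the consequence: nothing is lost unless a site follows the footnote over the text. It does not remove the error. Correct wording elsewhere shows which statement is wrong, but the wrong one remains in a table that sites are told to follow. Reading a visit after Period 2 as one after Period 3 is strained, because it leaves the footnote with no purpose. A complete column heading would only make Table 2 contradict itself.

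**Conclusion.** The concern holds. Footnote 1 is wrong as written for every Part 1B participant, at least 12 of whom are planned as evaluable, and right only for someone whose last dose is in Period 2. The size of the problem is conditional on a site acting on the footnote, in which case the gaps in step 3 of the working apply. Unscheduled pregnancy tests remain possible under Appendix 6. No estimate, model or sample size is affected. The discharge and footnote 11 discrepancies are clerical and have no effect on PK sampling or analysis.

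**What to change.** Replace footnote 1, in Protocol Table 2 and in its copy in SAP 14.2.1, with wording such as: *Follow-up takes place 7 to 14 days after the participant's final GSK2838232 dose, whichever treatment period that is.* This also covers participants who stop after Period 2.

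As minor corrections in the same edit, move the discharge mark to Day 6 after the 120 h sample, remove the outpatient marks on Days 3 to 6, and make footnote 11 refer to all study periods.

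The cost is schedule wording in two places, with no change to design, sample size or analysis.
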